5.3.6.2 Definitions of Variations in Surgical Performance

The following will be considered minor surgical variations:

- Failure to perform a frozen section of bile duct or pancreatic neck margins at the time of surgery.
- Documentation of an incomplete dissection of uncinate off the SMA.
- Documentation of a lymphadenectomy less extensive than that described above.

5.3.6.3 Surgical Quality Control

For all patients who undergo surgery during protocol treatment (including resection or not), the study chair and surgical co-chair will review the preoperative CT scan, the operative note, the surgical pathology report, and the adverse events associated with surgery (30 days postoperative) within 60 days of surgery. This requires that the study team complete the adverse event case report form (AE CRF) without delinquency.

Specific attention will be paid to deviations as listed above, as well as adverse events that occur in association with surgery. Operative reports and outcomes which, in the opinion of the study chair and surgical co-chair, raise potential patient safety concerns will be discussed and reviewed. Two operations which lead to such a discussion may lead to a surgeon being restricted from enrolling future patients.

5.4 Post-operative therapy

Post-operative chemotherapy for up to 2 months is allowed after recovery from surgery based on the primary treating physicians discretion.

5.5 General Concomitant Medication and Supportive Care Guidelines

In general, concomitant medications and therapies deemed necessary for the supportive care (such as anti-emetics, anti-diarrheal) and safety of the participant are allowed. This includes growth factor support for prevention of neutropenia. Myeloid growth factors will be used prophylactically, and all patients should receive pegfilgrastim or approved biosimilar 6mg SC x1, 0 to 72 hours after disconnecting from CI 5-FU as clinically indicated per institutional standard of care.

The participant must be asked to notify the investigational team about any new medications they take after the start of the study treatment. In the event that an Adverse Event occurs, the investigational team must record any concomitant medications related to this event on the appropriate Case Report Forms.

Acute allergic reactions will be treated per institutional standards. In the event of anaphylactic reaction, this includes any therapy necessary to restore normal cardiopulmonary status.

There is no known effect of NIS793 on the cytochrome P450 system, but the case report form must capture the concurrent use of all other drugs, over-the-counter medications, or alternative

therapies. The PI should be alerted if the participant is taking any agent known to affect or with the potential to affect selected CYP450 isoenzymes.

5.6 Criteria for Taking a Participant Off Protocol Therapy

Duration of therapy will depend on individual response, evidence of disease progression and tolerance. In the absence of treatment delays due to adverse event(s), treatment may continue for *8 cycles (each consisting of 14 days as noted above)*, followed by Radiation (if applicable) and Surgery, or until one of the following criteria applies:

- Disease progression
- Intercurrent illness that prevents further administration of treatment
- Unacceptable adverse event(s)
- Participant demonstrates an inability or unwillingness to comply with the medication regimen and/or documentation requirements
- Participant decides to withdraw from the protocol therapy
- General or specific changes in the participant's condition render the participant unacceptable for further treatment in the judgment of the treating investigator

Participants will be removed from the protocol therapy when any of these criteria apply. The reason for removal from protocol therapy, and the date the participant was removed, must be documented in the case report form (CRF). Alternative care options will be discussed with the participant.

When a participant is removed from protocol therapy and/or is off of the study, the participant's status must be updated in OnCore in accordance with REGIST-OP-1.

5.7 Duration of Follow Up

Participants will be followed until (1) initiation of a new regimen of anti-neoplastic therapy, (2) first disease progression event after removal from protocol therapy, or (3) until death. Tumor

assessments should continue to be performed every 12 weeks on these participants until first disease progression event, new regimen of anti-neoplastic therapy, or until death, whichever occurs first.

Participants removed from protocol therapy for unacceptable adverse event(s) will be followed until resolution or stabilization of the adverse event.

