5.8 Criteria for Taking a Participant Off Study

Participants will be removed from study when any of the following criteria apply:

- Lost to follow-up
- Withdrawal of consent for data submission
- Death
- At the discretion of the investigator

The reason for taking a participant off study, and the date the participant was removed, must be documented in the case report form (CRF). In addition, the study team will ensure the participant's status is updated in OnCore in accordance with REGIST-OP-1.

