9 BIOMARKER, CORRELATIVE, AND SPECIAL STUDIES

The following planned exploratory correlative studies are required at all participating sites. Please refer to study-specific Correlative Lab Manual for complete details.

RNA and DNA sequencing data will be shared with collaborating investigators for correlative science research. Original sequencing data will be shared with collaborators, but all samples will be de-identified and labeled with anonymized coding. In addition, all original data will be uploaded to the appropriate NCBI archive (i.e. GEO, dbGAP, SRA) as directed by grant funding and publication rules.

In addition to the tumor and blood samples, data collected will include known tumor histopathology features including site the tumor was obtained from, tumor type, grade, TMN staging, receptor status, and molecular features (using our Oncopanel, FISH and IHC analysis, and/or future clinical genotyping platforms), as well as patient age and any known mutational status. Mutational data collection will be incorporated in correlative sample analysis. Tissue obtained per the Correlative Lab Manual may be cultured in vitro in order to derive primary tumor and non-tumor cell lines to be used for subsequent biomarker, genotyping and preclinical drug evaluation studies by the study investigators.

Peripheral blood will be collected for each patient at multiple time points: prior to initiation of and during systemic therapy, prior to surgery, and every 6 months during the 2 years post-surgery. A surgical resection specimen after completion of neoadjuvant treatment on each arm – or a biopsy if surgery is not completed – will be collected for clinical and correlative study purposes.

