10 STUDY CALENDAR

Baseline evaluations (vital signs, physical exam, ECOG performance status) are to be conducted within 2 weeks prior to start of protocol therapy. Informed consent, tumor assessment by imaging, laboratory evaluation, echocardiogram, and EKG must be done \leq 4 weeks prior to the start of therapy. If the participant's condition is deteriorating, laboratory evaluations should be repeated within 48 hours prior to initiation of the next cycle of therapy. Assessments must be performed prior to administration of any study agent. Study assessments and agents should be administered within \pm 3 days of the protocol-specified date, unless otherwise noted.

	Screening*	Day 1 of each cycle of chemotherapy**	RT***	Surgery ****	Off Tx*****	Post Tx Follow-up*****	EDC Timepoints
FOLFIRINOX ^{A,B}		X					
NIS793 ^{C,D}		X					
Fluorouracil ^E			X				
Informed Consent	X						N/A
Tests & Observations							
Medical History	X						N/A
Concurrent Medications ^a	X						N/A
Physical Exam ^b , Vital Signs ^c	X	X	X	X	X	X	N/A
Height	X						N/A
ECOG Performance Status	X	X	X	X	X	X	Prior to registration, Day 1 of every cycle, prior to radiation, surgery, Off treatment
Adverse Event Assessment [†]		X	X	X	X	X	All visits
Laboratory Studies							
CBC, Differential, Platelets ^{d,f}	X	X	X	X	X	X	N/A
Serum Chemistry ^{e,f}	X	X	X	X	X	X	N/A
HIV, Hepatitis B/C serologies	X						
Pregnancy Test	X	X ^r					N/A
CA 19-9, CEA ^g	X	X	X	X	X	X	N/A
EKG ^h	X	X					N/A
Troponin I, NT proBNP ⁱ	X	X					N/A
Echocardiogram or MUGA or cardiac CT/MRI ^j	X						Prior to registration. Thereafter only if clinically indicated &/or if cardiac enzymes are elevated
Tumor Measurements ^k	X		X	X		X	Prior to registration, every 8 weeks on chemotherapy, prior to radiation, prior to surgery
Pathology Review ^{l,m}				X			
Optional tumor biopsy ⁿ	X				X		Prior to registration at baseline and at time of progression.
Archival tumor sample ^o	X						Prior to registration at baseline.
Research blood ^p	X	X	X	X ^q	X	X	Prior to registration, Day 1 of all chemotherapy, Prior to radiation, prior to surgery, off treatment

A: Fluorouracil 2400mg/m² IV on days 1 over 46 hours; Leucovorin 400mg/m² on day 1; Irinotecan 150mg/m² IV on day 1; Oxaliplatin 85mg/m² IV on day 1 of a 14 day cycle (+3/-1 days) for patients randomized to Arm A and B (See section 5.1).

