***** Post treatment follow up should be at least once every 12 weeks (+/- 28 days) until first disease progression event, new regimen of anti-neoplastic therapy, or until death, whichever occurs first. Participants removed from protocol therapy for unacceptable adverse event(s) will be followed until resolution or stabilization of the adverse event.

^a If new medications or changes are prescribed while patient is receiving treatment on study, these medications should be recorded.

^b A complete physical examination will be performed at baseline, prior to radiation and prior to surgery. A limited physical exam will be completed prior to therapy on Day 1 of the 8 cycles of chemotherapy +/- NIS793, and weekly during chemotherapy and radiation.

^c Vital sign assessments include measurements of heart rate, systolic and diastolic blood pressures, respiratory rate, temperature, and weight.

^d Hematology includes: hemoglobin, hematocrit, platelet count, RBC count, WBC count, and percent and absolute differential count. Results must be available prior to the administration of study drug. ANC must be ≥ 1500 for eligibility and Cycle 1 Day 1. Subsequent ANC must be ≥ 1000 .

^e Albumin, alkaline phosphatase, total bilirubin, bicarbonate, BUN, calcium, chloride, creatinine, glucose, LDH, phosphorus, potassium, total protein, SGOT [AST], SGPT [ALT], sodium.

^f Labs completed prior to registration may be used for day 1 of cycle 1 if obtained ≤ 7 days prior to treatment (except pregnancy test, CA 19-9, cea). Labs (hematology and serum chemistry) to be drawn every 2 weeks during chemotherapy, weekly during radiation, prior to surgery (+/- 2 weeks), and 2 weeks with the post-operative assessment.

^g Ca19-9 and CEA to be checked during screening, day 1 of all cycles of chemotherapy, prior to chemotherapy and radiation (+/- 2 weeks), prior to surgery (+/- 2 weeks), and at post-treatment follow up.

^h EKG will be performed at screening for all patients. Thereafter EKG is required on day 1 of each cycle of chemotherapy for *patients receiving NIS793*. QTc to be calculated using Bazzett's formula.

ⁱ Cardiac specific enzyme Troponin I and NT-proBNP will be checked on screening for all

patient and thereafter will be checked on C3D1 and day 1 of every third cycle during treatment duration or as clinically indicated, and at EOT visit for the patients randomized to the NIS793 arm.

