11.1.6 Progression-Free Survival

Overall Survival: Overall Survival (OS) is defined as the time from randomization (or registration) to death due to any cause, or censored at date last known alive.

Progression-Free Survival: Progression-Free Survival (PFS) is defined as the time from randomization (or registration) to the earlier of progression or death due to any cause. Participants alive without disease progression are censored at date of last disease evaluation.

Time to Progression: Time to Progression (TTP) is defined as the time from randomization (or registration) to progression, or censored at date of last disease evaluation for those without progression reported.

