13.2 Sample Size, Accrual Rate and Study Duration

Based on the DFCI and MDACC experience, the accrual duration is projected to be 36 months to enroll a total of 45 patients who receive protocol therapy. Patients will be followed actively for 5 years or until disease progression or initiation of an alternative anti-cancer therapy and thereafter

for survival.

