13.6 Analysis of Secondary Endpoints

- Progression free survival time is defined as the time period from the date of randomization to the date of disease progression, recurrence after surgery or death from any cause whichever occurs first.
- The overall survival time is defined as the time duration from randomization till death or last follow-up if the patient is alive.

The distributions of overall survival and progression free survival will be estimated using the Kaplan-Meier method. Comparisons of these time-to-event endpoints by important covariate subgroups will be made using the log-rank tests. Cox proportional hazards regression models will be explored to evaluate the associations between the time-to-event endpoints and covariates of interest.

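### Section 5.7 and the study calendar stop follow-up at progression or new therapy, section 13.2 continues it for survival, and no survival contact is scheduled; followed literally, OS would be informatively censored

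*Combined protocol and SAP*

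**What the plan says.** Four parts of the protocol bear on how long patients are followed.

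- **Section 5.7:** "Participants will be followed until (1) initiation of a new regimen of anti-neoplastic therapy, (2) first disease progression event after removal from protocol therapy". Death is the third listed event. A separate sentence then sets the 12-weekly tumor assessments and their stopping events.
- **Section 10, post-treatment footnote:** follow-up at least every 12 weeks "until first disease progression event, new regimen of anti-neoplastic therapy, or until death, whichever occurs first".
- **Section 13.2:** "Patients will be followed actively for 5 years or until disease progression or initiation of an alternative anti-cancer therapy and thereafter" for survival.
- **Section 5.8:** "Participants will be removed from study when any of the following criteria apply", listing loss to follow-up, withdrawal of consent for data submission, death and investigator discretion. Progression and new therapy are not on the list.

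OS is defined twice. Section 11.1.6 runs it from randomization (or registration) "to death due to any cause, or censored at date last known alive". Section 13.6 says: "The overall survival time is defined as the time duration from randomization till death or last follow-up if the patient is alive".

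The only other long-term contact is research blood, which section 9 plans "prior to surgery, and every 6 months during the 2 years post-surgery". The calendar's EDC timepoints for that item are: "Prior to registration, Day 1 of all chemotherapy, Prior to radiation, prior to surgery, off treatment".

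**The concern.** Sections 5.7 and 10 are what a site works from day to day, and both end follow-up at progression or a change of therapy. The promise to continue for survival appears only in the statistics section, without an interval, a method or an end date. The calendar has no survival-status row, and its EDC column names no survival timepoint.

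Kaplan-Meier, log-rank and Cox methods (section 13.6) need censoring to be unrelated to the risk of death. Progression and the start of another regimen both predict death. Ending observation there would usually bias the OS curve upward, and most deaths would never enter the database. Sites that read the text differently would also ascertain deaths unevenly.

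**Working it through.** **Reading the passages together**

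1. The first sentence of 5.7 cannot be limited to scans, because the next sentence sets the scan rule separately.
2. 13.2 names the same two events but makes them the end of active follow-up only. The end points therefore differ.
3. 5.8 keeps a progressed patient on study, so survival follow-up is permitted. Nothing schedules it.
4. If 5.7 is applied, the last follow-up in 13.6 becomes the date of progression or new therapy. 11.1.6 allows any later date on which the patient is known to be alive, but no contact is planned that would supply one.
5. Research blood after surgery covers resected patients only, for 2 years.

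**Size if 5.7 is applied literally**

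The plan gives no OS event count, power or effect size, so there is no figure of its own to reproduce. The following is an illustration.

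Inputs:
- Exponential PFS with median m = 10 months (assumed) or 13.4 months (the DFS figure in 2.1, from resected patients given adjuvant therapy).
- Share f of PFS events that are deaths without progression: 0.05, 0.10 or 0.20 (assumed).
- Median OS M = 35.0, 37.7 or 54.4 months (figures cited in 2.1).
- 45 patients (15 in Arm B), 60 months of observation each.

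Formulas, with h = ln 2 / m and g the constant hazard of death after progression:
- True OS(t) = exp(-ht) + [(1-f)h/(g-h)] × [exp(-ht) - exp(-gt)], with g solved so that OS(M) = 0.5.
- Kaplan-Meier OS at 24 months when follow-up ends at progression = exp(-24fh).
- Deaths by 60 months: 45 × (1 - OS(60)). Deaths recorded: 45 × f × (1 - exp(-60h)).

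Worked case, m = 13.4, f = 0.10, M = 37.7:
- h = 0.6931/13.4 = 0.05173. Solving gives g = 0.03367 (post-progression median 20.6 months).
- OS(24) = 0.289 + [0.9 × 0.05173/(0.03367 - 0.05173)] × (0.289 - 0.446) = 0.693.
- Kaplan-Meier stopped at progression = exp(-24 × 0.10 × 0.05173) = 0.883, an overstatement of 19 points.
- 32.8 deaths occur and 45 × 0.10 × (1 - exp(-60 × 0.05173)) = 4.3 are recorded. A simulation of 400,000 patients gave the same 0.693, 32.8 and 4.3.

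All 18 combinations:

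| Median OS (months) | True OS at 24 months | KM stopped at progression | Difference | Deaths of 45 by 60 months | Recorded |
|---|---|---|---|---|---|
| 35.0 | 0.640–0.674 | 0.717–0.940 | +0.077 to +0.266 | 32.6–34.8 | 2.1–8.9 |
| 37.7 | 0.659–0.702 | 0.717–0.940 | +0.058 to +0.238 | 31.0–33.2 | 2.1–8.9 |
| 54.4 | 0.730–0.805 | 0.717–0.940 | -0.013 to +0.135 | 24.0–24.6 | 2.1–8.9 |

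In Arm B, 8.0–11.6 deaths of 15 would occur and 0.7–3.0 be recorded.

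The one negative cell is m = 10, f = 0.20, M = 54.4. There the hazard of death before progression, fh = 0.20 × 0.06931 = 0.0139, exceeds the solved post-progression hazard of 0.0122, so stopping at progression removes the lower-risk period.

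**Second set of assumptions**

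A separate simulation used PFS medians of 10–18 months, post-progression medians of 9–24 months, f of 0.05–0.20 and 60–96 months of observation. True 36-month OS was 0.23–0.64 against 0.61–0.93 under the literal rule. About 33–44 deaths of 45 were observed with full follow-up and 2–9 without. The bias was upward in every scenario.

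**The case against.** The best defence is that the plan largely answers the point itself. 13.2 states the intent, 5.8 keeps progressed patients on study, and 11.1.6 censors OS at the last date known alive. The calendar footnote can be read as setting only the clinic visits with examinations, laboratory tests and scans, which 13.2 calls active follow-up. In 5.7 the first-of-several wording is attached to tumor assessments only. 5.8 also requires a death to be documented on the CRF and in OnCore. The research-blood row is marked in the post-treatment column, whatever its EDC entry says. The two OS censoring rules normally give the same date.

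Much of this is fair, and it is why the bias is conditional. It does not close the gap. Section 5.8 records a death that the site learns of but schedules no contact to learn of it. The post-treatment column carrying the blood mark itself ends at progression or new therapy. The two censoring rules diverge exactly when 5.7 is followed.

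The criticism of the numbers also stands in part. They pair a DFS figure and OS medians from different populations, and f is assumed. The 54.4-month cells imply post-progression medians of 36–57 months, for which the documents give no support. The model stops at any first progression, as the footnote does, whereas 5.7 refers to progression after removal from protocol therapy. The sizes are illustrative; the loss of most deaths is common to every scenario.

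**Conclusion.** The concern holds. Sections 5.7 and 10 contradict 13.2 on when follow-up ends, and the survival follow-up that 13.2 promises is not scheduled anywhere. This should be fixed, because a rule followed as written would damage a named secondary endpoint.

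If 5.7 is applied literally, and under the assumptions above, roughly 2–9 deaths would be recorded instead of 24–35 of 45 by 60 months. OS at 24 months would usually be overstated: by 6 to 27 points at median OS of 35.0–37.7 months, and by -1 to 13 points at 54.4 months. Follow-up ended by new therapy before progression is not modelled and would lose more deaths. If sites follow 13.2, this bias does not arise. The MPR analysis is unaffected in either case.

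**What to change.** 1. In 5.7 and the calendar's post-treatment footnote, state that progression and new anti-neoplastic therapy end active follow-up and tumor assessments only, and that survival follow-up then continues as in 13.2.
2. Add a survival-status row and EDC timepoint to the calendar, by telephone or chart review, for example at the existing 12-week interval. It should apply to every patient regardless of resection, progression or later therapy, and run to death, loss to follow-up, withdrawal of consent for data submission or a stated end date. Give that end date in 13.2.
3. Use one OS censoring rule: change 13.6 to the date last known alive, as in 11.1.6.

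The cost is wording in 5.7, 13.2, 13.6 and the calendar, one EDC field, and brief status checks for at most 45 patients, which 13.2 already commits to.

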Multiple small phase II studies have evaluated the role of neoadjuvant therapy utilizing a range of chemotherapeutic agents. One study which evaluated FOLFORINOX and radiation in 48 patients with borderline-resectable pancreatic cancer demonstrated a median OS of 37.7 months (95% CI, 19.4 to not reached)(16). Three trials that have compared multi-modality neoadjuvant therapy to surgery followed by adjuvant therapy. The phase III PREOPANC trial compared outcomes with preoperative chemoradiotherapy vs immediate surgery for *resectable or borderline resectable* pancreatic cancer. Chemoradiotherapy consisted of 3 cycles of gemcitabine, combined with 15 fractions of 2.4 Gy radiotherapy. Disease-free survival, locoregional failure-free survival, R0 resection rate (71% v 40%), and pathologic response favored neoadjuvant therapy. PEROPANC used a dated chemotherapy regimen at a modest dose (23), however, the ESPAC-5f trial is comparing upfront surgical exploration for *borderline resectable* pancreatic cancer, to gemcitabine plus capecitabine (GEMCAP), or FOLFIRINOX or 50.4Gy capecitabine-based CRT.(24) Initial results demonstrated survival rates for the specific neoadjuvant regimens were 84% for FOLFIRINOX, 79% for GEMCAP and 65% for CRT (25). In the third trial, Alliance A021501, patients were randomized to either neoadjuvant mFOLFIRINOX or mFOLFIRINOX followed by radiation therapy. Patients who received radiation therapy did not have improved survival and had numerically lower rates of R0 pancreatectomy (42% vs 25%), initiation of postop therapy (33% vs 24%) and completion of all treatment (30% vs 18%). 64% of patients in this study had ≥ 1 grade 3+ adverse events, and 17% had ≥ 1 grade 4+ adverse events (26).

Several radiation regimens have also been utilized. Apart from the trials described above, trials have used regimens such as FOLFIRINOX followed by either short-course chemoradiotherapy (5 Gy \times 5 with protons) with capecitabine or long-course radiotherapy (50.4 Gy in 28 fractions) with capecitabine or continuous 5FU (15, 16). Some centers also apply intraoperative radiation therapy

(IORT) to improve local control (27). Others utilize MRI-guided radiation therapy (28).

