B: Subcutaneous growth factor support will be administered between 0 and 72 hours after discontinuation of continuous infusion of 5-FU in all patients receiving FOLFIRINOX after each cycle. Participants may self-administer at home or have the injection administered in clinic.

C: NIS793 2100mg IV on day 1 of a 14-day cycle (+3/-1 days) for patients randomized to Arm A (See section 5.3)

D: The first five patients randomized to NIS793 (Arm A) will be part of a safety lead-in. Study will pause until the last patient accrued for safety lead-in has completed two full treatment cycles (i.e., 28 days). Participants must have received at least 75% of their assigned doses of FOLFIRINOX and NIS793 to be considered evaluable for this safety analysis, unless dosing was held or reduced due to toxicity. If one or more of the first five participants enrolled does not meet this parameter for a reason other than toxicity (e.g. rapid disease progression and subsequent removal), Arm A will continue to accrue as many participants as needed to have five evaluable participants for safety assessment.

E: Capecitabine twice daily on days of radiation OR Fluorouracil by continuous infusion on days of radiation. Doses to be determined by institutional standards and physician discretion but the recommended doses are 5FU 225mg/m²/day continuous infusion Monday-Friday, Capecitabine 1650mg/m²/day po.

* Screening evaluation (vital signs, physical exam, ECOG performance status) are to be conducted within 2 weeks of starting protocol therapy. Informed consent, tumor assessment by imaging, laboratory evaluation, echocardiogram, and EKG must be done <= 4 weeks prior to start of therapy.

** Drug dosages to be modified due to changes in body weight or body surface area (BSA) based on institutional criteria. If no such criteria exist recalculate doses when there is a greater than 10% change in weight or BSA.

*** RT only delivered for patients with borderline resectable PDAC. Radiation planning visit should occur at the time of Cycle 7 of treatment. Assessments should be done approximately weekly, and at least once for every five fractions of radiation.

**** Surgical assessments should be done once within 14 days prior to the operation.

***** End of treatment appointment to be performed within 4 weeks of the last study treatment event. Performed prior to the initiation of any non-study related cancer therapies.

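### Tumor imaging stops at an undefined new anti-neoplastic regimen that the PFS definition ignores, and no section says whether Section 5.4 post-operative chemotherapy counts as one

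*Combined protocol and SAP*

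**What the plan says.** **Stop rules.** Section 5.7 opens with "Participants will be followed until (1) initiation of a new regimen of anti-neoplastic therapy" as one of its end points, then says that tumor "assessments should continue to be performed every 12 weeks on these participants until first disease progression event, new regimen of anti-neoplastic therapy" or death. The Study Calendar footnote on post-treatment follow-up has the same trigger: visits run "until first disease progression event, new regimen of anti-neoplastic therapy, or until death, whichever occurs first". Section 13.2 ends active follow-up at progression or an alternative anti-cancer therapy, and continues for survival after that.

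**Post-operative chemotherapy.** Section 5.4 reads "Post-operative chemotherapy for up to 2 months is allowed after recovery from surgery based on the primary treating physicians discretion". It names no regimen. Section 5.6 lists the treatment course as eight cycles, radiation where applicable, and surgery; post-operative chemotherapy is not in that list. The calendar has no column for it, and the end-of-treatment visit is to be "Performed prior to the initiation of any non-study related cancer therapies".

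**Scans after surgery.** Calendar footnote k, attached to the Tumor Measurements row, schedules a scan every 12 weeks (within 28 days either way) after surgery. It gives no stop rule.

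**PFS.** Section 13.6 counts progression, recurrence after surgery or death from any cause. Section 11.1.6 adds: "Participants alive without disease progression are censored at date of last disease evaluation". Neither section censors at the start of new therapy.

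**The concern.** The endpoint and the data collection follow different rules. PFS is defined irrespective of later therapy, but the scans needed to observe it stop when later therapy begins. For a patient who has not progressed, the plan stops looking for an event that it still defines.

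This matters most after resection. Section 5.4 expressly permits chemotherapy at that point, and whether it is a new regimen is left open. Patients who receive it have reached surgery, recovered and been judged fit for more treatment, so losing their scans is unlikely to be independent of prognosis. Treatment is unblinded (Section 5.1) and the choice is the physician's, so the pattern could differ between arms. It could also differ between sites, because each has to decide which reading applies.

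PFS is a stated secondary objective (Section 1.3.2). Scans not taken cannot be recovered later.

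**Working it through.** The plan gives no PFS sample size, event count, median or hazard ratio, so there is no PFS figure to reproduce. The check is a timeline, a comparison of readings, and a count of exposed patients.

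**1. Timeline, resectable disease, from the start of chemotherapy.**
- Induction (Section 5.3.2): 8 cycles × 14 days = 112 days = 16 weeks.
- Surgery 2 to 8 weeks later (Section 5.3.6): 16 + 2 = week 18 to 16 + 8 = week 24. Borderline resectable patients have radiation first, so surgery is later.
- Pre-operative scan (footnote k): within about 2 weeks of surgery.
- First post-operative scan (footnote k): 12 weeks ± 28 days = 12 ± 4 = 8 to 16 weeks after surgery, that is week 18 + 8 = 26 to week 24 + 16 = 40.

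Section 5.4 gives no start date beyond recovery from surgery. If chemotherapy starts before the first post-operative scan and is read as a new regimen, the last scheduled evaluation is the pre-operative one. Section 11.1.6 then censors a living patient at about the time of surgery.

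**2. The two readings.**

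| Post-operative chemotherapy is a new regimen | It is permitted trial care |
|---|---|
| Section 5.6 does not list it in the treatment course | Section 5.4 sits in the Treatment Plan, and Section 5.1 bars only therapies not described there |
| No calendar column for it | Footnote k schedules post-surgical scans with no stop rule |
| Sections 5.7 and the follow-up footnote make no exception | With no regimen named, it could be the same drugs resumed |

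No section chooses between them.

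**3. Effect on PFS if imaging stops.** Take an event-free resected patient who starts Section 5.4 chemotherapy.
- *Recurs, alive at analysis:* censored near surgery; the event is lost.
- *Recurs, then dies:* survival follow-up under Section 13.2 records the death, and death from any cause is a PFS event, so the event is dated at death instead of at recurrence. PFS looks longer.
- *Never recurs:* censored near surgery; the later event-free time is lost. If these patients do better than the rest, PFS looks shorter.

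The effects oppose one another, and the documents give no rates with which to net them.

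**4. Patients exposed.** Section 2.1 quotes a randomized trial in which post-operative therapy was started in 33% and 24% of its two arms. Assume those rates apply to all randomized patients here:
- Total: 0.24 × 45 = 10.8 and 0.33 × 45 = 14.9, about 11 to 15 of 45.
- Arm A: 0.24 × 30 = 7.2 and 0.33 × 30 = 9.9, about 7 to 10 of 30.
- Arm B: 0.24 × 15 = 3.6 and 0.33 × 15 = 5.0, about 4 to 5 of 15.

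The reference list shows that the cited trial enrolled borderline resectable disease only. This trial also enrolls resectable disease, so the true share may differ. These counts are patients exposed to the ambiguity, not a measure of bias.

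**The case against.** The strongest reply is that the plan does not order sites to stop imaging at post-operative chemotherapy. Footnote k governs the tumor measurement row and has no stop rule. Section 13.2 ends active follow-up without mentioning scans. Its trigger is an alternative therapy, and the end-of-treatment footnote speaks of therapy outside the study; treatment that Section 5.4 allows is naturally neither. Section 13.6 counts recurrence after surgery, and Section 9 plans research blood for 2 years after surgery, so longer follow-up was intended. All of this stands. It shows that the defect is an ambiguity; it does not remove it, because Section 5.7 and the follow-up footnote still end assessment at an undefined trigger.

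It is also fair that PFS is secondary, with no sample size or formal between-arm hypothesis. Section 13.6 plans Kaplan-Meier estimates, log-rank tests by covariate subgroup and exploratory Cox models. That limits the weight of the point.

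Three stronger inferences are tempting, and the documents do not support them:
- *PFS would be understated by a calculable amount.* Any such figure has to assume that exposed patients contribute no later event, but their deaths still count.
- *Most recurrences would fall after imaging stops.* The documents give no recurrence timing.
- *A patient with metastasis found at an aborted resection would be censored as progression-free.* Section 11.1.4 already treats a new lesion as progression, and Section 13.6 does not limit progression to imaging. How that event is dated is at most a matter for clarification.

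**Conclusion.** The concern holds as a mismatch between assessment rules and endpoint. Tumor assessment stops at a new regimen without progression, while PFS ignores new therapy and depends on those assessments. Whether Section 5.4 chemotherapy triggers the stop is undefined, so sites may differ.

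Under the stopping reading, and if chemotherapy starts before the first post-operative scan, resected event-free patients would be censored near surgery or given an event only at death. About 11 to 15 of 45 could be exposed if the quoted rates carry over. The censoring may be informative, but its direction and size cannot be established from the documents.

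MPR is read at surgery and is unaffected. OS is unaffected provided that survival follow-up continues as Section 13.2 states. The change is advisable; the primary conclusion does not depend on it.

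**What to change.** 1. Reconcile Sections 5.4, 5.7 and 13.2 with the two calendar footnotes. State that post-operative chemotherapy given under Section 5.4 does not end the 12-weekly tumor assessments.
2. For the main PFS analysis, continue the scheduled assessments to progression, recurrence or death regardless of any new anti-neoplastic therapy. Say so in Sections 11.1.6 and 13.6.
3. Record the start date of any new therapy and pre-specify censoring at that date as a sensitivity analysis.
4. Optionally, add a line on how metastatic disease found at exploration is dated for PFS.

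The cost is protocol wording and some extra retrieval of scans, on a schedule already in the plan. No treatment changes. The wording should be settled before patients reach the post-operative period.
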